•	To compare LY2951742 with placebo with respect to change in global severity of migraine condition	•	The mean change from baseline in the Patient Global Impression of Severity (PGI-S) score (average of Months 4, 5, and 6)
Ot	her Secondary Objectives		
•	To compare LY2951742 with placebo with respect to change in headache days	•	The overall mean change from baseline in the number of monthly headache days during the 6-month double-blind treatment phase
•	To compare LY2951742 with placebo with respect to change in moderate to severe headache days	•	The overall mean change from baseline in the number of monthly moderate to severe headache days during the 6-month double-blind treatment phase
•	To compare LY2951742 with placebo with respect to a 30% response rate	•	The proportion of patients with reduction from baseline $\geq 30\%$ in monthly migraine headache days during the 6-month double-blind treatment phase
•	To compare LY2951742 with placebo with respect to distribution of response rates	•	Cumulative distribution of monthly migraine headache day response rates during the 6-month double-blind treatment phase
•	To compare LY2951742 with placebo with respect to time to 50% response	•	Time to first occurrence of a ≥50% reduction from baseline in the number of monthly migraine headache days (Kaplan-Meier analysis)
•	To compare LY2951742 with placebo with respect to onset of effect	•	The initial month at which statistical separation in mean change from baseline in the number of monthly migraine headache days is demonstrated and maintained at all subsequent months through Month 6
•	To compare LY2951742 with placebo with respect to onset of 50% sustained response	•	The initial month at which statistical separation in the proportion of patients meeting at least a 50% reduction in monthly migraine headache days that is maintained at all subsequent months through Month 6

Table CGAH.1. Objectives and Endpoints (continued)

Objectives (cont.)	Endpoints (cont.)	
Other Secondary Objectives (cont.)  To compare LY2951742 with placebo with respect to maintenance of 50% response	The proportion of patients who maintain 50% response criteria for at least 3 consecutive months to the end of the double-blind treatment phase and the proportion of patients who maintain 50% response criteria for 6 consecutive months during double-blind treatment	

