**Study Period III**: At the start of the 6-month double-blind treatment phase (Visit 3), patients meeting all eligibility requirements will be randomized to 1 of 3 treatment groups in a 2:1:1 ratio to receive placebo, 120 mg/month LY2951742, or 240 mg/month LY2951742, respectively.

Patients randomized to the 120 mg dose of LY2951742 will receive an initial loading dose of 240 mg (2 injections of 120 mg each at Visit 3 only). To preserve blinding throughout the study, patients in all treatment groups will receive 2 injections of investigational product at each dosing visit (two placebo injections, two 120-mg LY2951742 injections, or one placebo injection and one 120-mg injection). At Visit 3, if available and where local regulations and Ethical Review Boards allow, patients will also watch a training video designed to address patient expectations with regard to participation in a placebo-controlled trial and the difference between medical treatment and research.

The patient will be considered enrolled in the study when randomization occurs. During this phase, study procedures at dosing visits must always occur prior to the patient receiving their assigned treatment.

Patients will be given injections of investigational product during office visits (Figure CGAH.1). For all treatment groups, subcutaneous injections will be administered once monthly at the dosing visits. At Visit 3 (first dose), patients will be required to remain in the office for observation for 30 minutes post injection. Patients will continue to log in and complete the ePRO diary each day. Patients may continue to take their allowed acute migraine headache medication (with some limitations; see Section 6.8) during the treatment phase.

Patients who complete this phase or discontinue for any reason during Study Period III will be expected to enter post-treatment follow-up (Study Period IV).

**Study Period IV**: During this 4-month phase, sites and patients will remain blinded to patients' treatment assignments. Patients will follow all study procedures during Study Period IV but will not receive LY2951742 or placebo. One month after Visit 12, if clinically warranted due to a worsening of symptoms, patients may start migraine prevention medications at the discretion of

the investigator. The list of allowed preventive medications is provided in Section 6.8. At Visit 14 (Month 10), patients will return to the site for their last study visit and discharge from the study.

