4.2.2. Other Secondary Objectives

The secondary objectives listed below in Table 4.2 reflect the comparison of LY2951742 (120 or 240 mg/month) with placebo. No multiplicity adjustment will be implemented for the secondary objectives.

Table 4.2. List of Other Secondary Objectives and Their Endpoints

Other Secondary Objectives	Endpoints
To compare LY2951742 with placebo with respect to change in headache days	The overall mean change from baseline in the number of monthly headache days during the 6-month double-blind treatment phase
To compare LY2951742 with placebo with respect to change in moderate to severe headache days	The overall mean change from baseline in the number of monthly moderate to severe headache days during the 6-month double-blind treatment phase
To compare LY2951742 with placebo with respect to 30% response rate	The proportions of patients demonstrating ≥30% reduction from baseline in the number of monthly migraine headache days during the 6-month double-blind treatment phase
To compare LY2951742 with placebo with respect to distribution of response rates	Cumulative distribution of monthly migraine headache day response rates during the 6-month double-blind treatment phase
To compare LY2951742 with placebo with respect to time to first 50% response	Time to first occurrence (in months) of a ≥50% reduction from baseline in the number of monthly migraine headache days (Kaplan-Meier analysis)
To compare LY2951742 with placebo with respect to onset of effect	The initial month at which statistical separation in mean change from baseline in monthly migraine headache days is demonstrated and maintained at all subsequent months through Month 6
To compare LY2951742 with placebo with respect to onset of 50% sustained response	The initial month at which statistical separation in the proportion of patients meeting at least a 50% reduction in monthly migraine headache days that is sustained at all subsequent months through Month 6
To compare LY2951742 with placebo with respect to maintenance of 50% response	The proportion of patients who maintain 50% response criteria for at least 3 consecutive months to the patient's endpoint during double-blind treatment phase. The proportion of patients who maintain 50% response criteria for 6 consecutive months during double-blind treatment phase

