- An X% responder is defined as Yes, if any patient who has a ≥X% reduction in the total number of migraine headache days in a 30-day period relative to baseline period, as No if otherwise. Therefore, if the percent change from baseline in the number of migraine headache days is ≥X%, the patient will be counted as an X% responder. In other words, if the response rate defined above in a month is ≥X%, then the patient will be an X% responder in that month. Indicators of X% responders will be derived for X=0, 5, 10, ..., 95, and 100.
- 50% responders sustained for at least 3 consecutive months to patient's endpoint in the double-blind treatment phase in the number of monthly migraine headache days is defined as meeting 50% responder criterion in the number of migraine headache days for 3 consecutive months to patient's endpoint in the double-blind treatment phase.
- 50% responders sustained for all 6 months during treatment phase in the number of migraine headache days is defined as meeting 50% responder criterion in the number of migraine headache days for Months 1-6 in the double-blind treatment phase.
- **Time to first 50% response (in months)** is defined as the first month when 50% response is met during double-blind treatment phase (SP III). If a patient has not met 50% response during SP III, they will be censored at the last month where 50% response status is not missing.

- Time to first loss of 50% response in the post-treatment phase (in months) is calculated for Month 6 50% responders as the time from the end of treatment phase to the first month in Study Period IV at which these patients no longer meet 50% response criteria. Patients who continue meeting the criteria until the end of the study will be censored.
- Time to initiation of treatment with a migraine preventive medication (in days) in the post-treatment phase is defined as the disposition date of previous study period before entering post-treatment follow-up phase minus the date of start of the migraine preventive medication (based on information collected from concomitant medication electronic case report form [eCRF]) in post-treatment follow-up phase (Study Period IV, SP IV). If a patient did not initiate preventive treatment during SP IV, they will be censored at the disposition date of SP IV. This analysis will be conducted only for patients who entered SP IV.

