For models where the unstructured covariance matrix is not utilized, the sandwich estimator (Diggle et al. 1994) will be used to estimate the standard errors of the fixed effects parameters. The sandwich estimator is utilized by the EMPIRICAL option in SAS. When the sandwich estimator is utilized, the Kenward-Roger approximation for denominator degrees of freedom cannot be used. Instead, the denominator degrees of freedom will be partitioned into between-subject and within-subject portions by the DDFM=BETWITHIN option in SAS.

For the repeated binary secondary efficacy measures where the objective is to assess the proportion of patients with X% response during the 6-month double-blind treatment phase, the endpoint for comparing LY2951742 with placebo will be estimated as the main effect of treatment from the categorical MMRM analysis across Months 1-6.

For visit wise indicators of 50% responders, the results of the statistical tests at each month in the double-blinded treatment phase from categorical MMRM analysis will be used to assess the onset of 50% sustained response for LY2951742 compared to Placebo. In particular, if the key secondary measure of 50% response rate is statistically significant, then the earliest month where the statistical significance is observed and maintained for all the subsequent months during double-blinded treatment phase will be considered as the onset of 50% sustained response.

For non-repeated binary measures, such as 50% response sustained for three consecutive months until patient's endpoint in 6-month treatment phase and 50% response sustained from Month 1 to Month 6, a logistic regression analysis with covariates of treatment, baseline and pooled region 1 will be conducted.

Measures Conditional on the Post-baseline Number of Migraine Headache Days > 0

The following measures are conditional on the number of migraine headache days >0:

- Mean severity of remaining migraine on migraine headache days
- Proportion of migraine headache days with abortive (acute) medication use

They will be modelled individually using MMRM model, assuming data are missing during months without migraine headache.

Analyses for Number of Weekly Migraine Headache Days in Month 1

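### Maintenance of 50% response runs to the end of the 6-month phase in the protocol but to an undefined patient's endpoint in the SAP, so a patient with three responding months who then leaves counts as maintained

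*SAP*

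**What the plan says.** Protocol Section 3, Table CGAH.1, lists under other secondary objectives "The proportion of patients who maintain 50% response criteria for at least 3 consecutive months to the end of the double-blind treatment phase". Protocol 4.1 gives that phase a length of 6 months.

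The SAP ends the run elsewhere, and does so consistently:

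- Table 4.2 (4.2.2): "at least 3 consecutive months to the patient's endpoint during double-blind treatment phase".
- Derivation (5.4.1): "meeting 50% responder criterion in the number of migraine headache days for 3 consecutive months to patient's endpoint in the double-blind treatment phase".
- Analysis by logistic regression (5.5.10.3): "50% response sustained for three consecutive months until patient's endpoint in 6-month treatment phase". Table 5.6 carries the same anchor.

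The SAP nowhere defines the patient's endpoint. The nearest convention is the LOCF rule in 5.5.1.5 and Table 5.5, which takes the last non-missing observation after Visit 3 and up to Visit 12.

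The companion 6-month endpoint is tied to calendar months: "meeting 50% responder criterion in the number of migraine headache days for Months 1-6 in the double-blind treatment phase".

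**The concern.** Maintenance is meant to show that a response lasts. If the run may end wherever a patient's data end, leaving the trial fixes a success that staying would put at risk. The reported proportion then includes patients who contributed nothing in the later months, and the two documents answer different questions under one endpoint name. At stake are the maintenance proportions in each arm and their comparison.

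**Working it through.** **1. What the protocol anchor means.** Three consecutive months ending with a 6-month phase are Months 4, 5 and 6. The SAP supports this. For loss of response in Study Period IV, the protocol takes patients who meet the criterion when the double-blind phase ends, and SAP 5.4.1 derives that group as the 50% responders at Month 6. So the SAP reads the end of the phase as Month 6 for one endpoint and uses another anchor for maintenance.

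**2. The two rules applied to individual patients**, with the patient's endpoint read as the last observed month:

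| Patient | Protocol anchor | SAP anchor |
|---|---|---|
| Responds in Months 1-3, leaves after Month 3 | no response shown in Months 4-6 | maintained |
| Responds in Months 1-5, stays, loses response in Month 6 | not maintained | not maintained |
| Responds only in Month 3, then leaves | not maintained | not maintained |
| Responds in Months 4-6, completes | maintained | maintained |

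Only the first type of patient is classified differently, together with those who leave after Month 4 or 5 with three responding months behind them.

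**3. Partial months.** SAP 5.4.1 sets a month to missing when diary compliance is 50% or less. For the last month of an early discontinuer the denominator is at least 30 days. With a denominator of 30, 16 diary days are usable, so exit during Month 3 can also qualify. Conversely, a patient who worsens and leaves in Month 4 with 15 or fewer diary days has Month 4 set to missing. The last observed month is then Month 3, and a loss that was partly observed can be scored as maintenance.

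**4. Size.** Inputs from SAP 5.2: 825 patients, 26% discontinuation, 611 completers. Check: 825 x (1 - 0.26) = 610.5, which agrees with 611. Neither the timing of dropout nor the share of dropouts with three responding months is given, so both are assumed.

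Patients classified differently = 825 x 0.26 x (share of dropouts leaving after Month 3) x (share of those responding in each of their last three months).

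| Share leaving after Month 3 | Patients exposed | 20% responding | 40% responding |
|---|---|---|---|
| 25% | 54 | 11 (1.3%) | 21 (2.6%) |
| 50% | 107 | 21 (2.6%) | 43 (5.2%) |
| 75% | 161 | 32 (3.9%) | 64 (7.8%) |

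The plan ties 26% to completing the study, which runs to Month 10. If dropout is even over 10 months, exits between Months 3 and 6 are 0.26 x 3/10 = 7.8% of patients (64 of 825). At 20-40% responding, that is 13 to 26 patients (1.6-3.1%).

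**5. Effect on the comparison.** Assume sustained response of 20% on placebo and 40% on active, half of dropouts after Month 3, and dropouts counted as failures under the protocol anchor. Protocol rate = response x (1 - dropout). SAP rate = response x (1 - dropout/2).

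| Dropout, placebo / active | Protocol rates | Difference, odds ratio | SAP rates | Difference, odds ratio |
|---|---|---|---|---|
| 26% / 26% | 14.8% v 29.6% | 14.8 points, 2.42 | 17.4% v 34.8% | 17.4 points, 2.53 |
| 30% / 22% | 14.0% v 31.2% | 17.2 points, 2.79 | 17.0% v 35.6% | 18.6 points, 2.70 |
| 22% / 30% | 15.6% v 28.0% | 12.4 points, 2.10 | 17.8% v 34.0% | 16.2 points, 2.38 |

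First row, odds ratios: (0.296/0.704)/(0.148/0.852) = 2.42 and (0.348/0.652)/(0.174/0.826) = 2.53. The risk difference grows in all three cases. The odds ratio, which the planned logistic regression estimates, hardly moves with equal dropout, falls slightly when placebo dropout is higher and rises when active dropout is higher.

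**The case against.** The strongest defence is that the protocol wording can be read per patient. Under Protocol Section 7, anyone who discontinues in Study Period III moves at once to Study Period IV, so that patient's double-blind phase ends there and the documents agree. This is possible but weak: the protocol describes a 6-month phase, and the SAP takes the end of the phase as Month 6 for loss of response.

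Other parts of the defence stand. Reading the patient's endpoint as the last observed month is an inference from the LOCF convention. The protocol does not say that dropouts count as failures; its anchor only implies it. The SAP states that it supersedes the protocol's statistical plans, Protocol 9.4.3 leaves details of other secondary analyses to it, and the strict 6-month companion endpoint is already planned. The choice of dropout rule is in part a choice of estimand.

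A reader might also infer that the anchor was changed late and without record, because the SAP revision history does not list it. The documents do not show that. The history lists changes between SAP versions; the wording may already have stood in Version 1, which is not available. Protocol 9.2 also allows a justification to appear in the study report.

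**Conclusion.** The two documents define this endpoint differently, and the SAP's anchor is undefined. Taken as the last observed month, it credits maintenance to patients with three responding months who leave before Month 6. The share classified differently is about 1.3-7.8% of 825 under the assumed ranges, and 1.6-3.1% if the 26% is spread evenly over 10 months. Only the 26% and the 825 come from the plan.

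Two stronger readings are not supported. Not every responder who drops out is counted; response is needed in each of the last three observed months. Nor do the documents show that the rule favours the active arms, or an arm whose responders leave for tolerability: they give no dropout or response by arm, and the illustration shifts the odds ratio in either direction.

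The endpoint is other secondary, without multiplicity adjustment. The primary and key secondary endpoints, the sample size and the 6-month maintenance endpoint are unaffected. The correction should be made, but it does not touch the trial's main conclusions.

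**What to change.** In SAP Table 4.2, 5.4.1, 5.5.10.3 and Table 5.6:

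- Define the main analysis as 50% response in Months 4, 5 and 6.
- State explicitly that patients who discontinue Study Period III before Month 6 count as not maintaining. Also state how a completer is scored when one of those months is missing for low diary compliance.
- Define the patient's endpoint, including the treatment of a partial last month, and keep that version as a sensitivity analysis.
- Record the difference from the protocol wording and the reason for it.

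The cost is SAP wording, one extra logistic regression, and somewhat lower reported maintenance rates in all arms. Protocol 9.2 allows SAP changes only before unblinding, so the change belongs before the second interim analysis.

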5.4.2. Other Efficacy Measures

5.4.2.1. Patient Global Impression

The Patient Global Impression of Severity (PGI-S) will be collected at baseline and monthly post-baseline visits. In this single-item scale, patients rate the severity of their migraine condition on a scale ranging from "not at all ill" (coded as 1) to "extremely ill" (coded as 7).

The Patient Global Impression of Improvement (PGI-I) will be collected at monthly post-baseline visits during the treatment phase.

Change from baseline in PGI-S scores will be analyzed. Patient Global Impression of Improvement scores at post-baseline visits will be analyzed by adjusting for PGI-S score at baseline.

5.4.2.2. Non-Migraine Chronic Pain Assessment

The Lilly-developed non-migraine chronic pain assessment (questions shown below) will provide exploratory information on any changes in non-migraine chronic pain conditions that patients may be experiencing. The following questions are to be collected:

Q1: Does the subject have any non-migraine chronic pain conditions?

- Yes
- No

If Yes, go to Q2 and Q3.

Q2:	What is	the	subject's	chronic	pain	condition?
_			3		1	

• AE Number: ____

Medical History Number:

Q3: In the past week, what was the subject's average pain score related to this condition?

- 0 No Pain
- 1-9 The patient would enter value of 1–9, and the bigger the number, the worse the pain.
- 10 Worst pain imaginable

The average pain score of all non-migraine chronic pain conditions will be derived for each subject by averaging the pain scores of all reported non-migraine chronic pain conditions. The mean change from baseline in the average pain score will be used as the analysis value.

If a specific non-migraine chronic pain condition is reported by more than 15% of the study population at baseline, the pain score of that specific condition will also be analyzed.

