To assess changes in efficacy outcomes during Study Period IV as collected by electronic patient- reported outcomes (ePRO) diary data	In Study Period IV:     Mean change from baseline in monthly migraine headache days     Time to first loss of response among patients who met the 50% response rate criteria at the end of the double-blind treatment phase     Time to initiation of treatment with a migraine prevention medication
Tertiary Objectives	
CCI	
To explore the effect of LY2951742 on non- migraine chronic pain	Mean change from baseline in average pain severity of other chronic pain conditions
To compare LY2951742 with placebo with respect to categorical changes in quality of life	
 
Percentages of patients with:         
 
≥50% improvement in MIDAS total score
 
change from baseline in MSQ Role Function-Restrictive domain ≥10.9
 
change from baseline in MSQ Role Function-Preventive domain ≥8.3
 
change from baseline in MSQ Emotional Function domain ≥12.2
 
 
 

Table CGAH.1. Objectives and Endpoints (continued)

Objectives (cont.)	Endpoints (cont.)
Tertiary Objectives (cont.)  To compare LY2951742 with placebo with respect to the proportion of migraine headache days requiring medication for the acute treatment of migraine or headache	Change from baseline in the proportion of monthly migraine headache days requiring medication for the acute treatment of migraine or headache
To compare LY2951742 with placebo with respect to changes in symptomatology associated with migraine or probable migraine	
 
Change from baseline in the number of monthly migraine headache days with:
 
nausea and/or vomiting
 
photophobia and phonophobia
 
aura
 
prodromal symptoms other than aura
 

 Table CGAH.2.
 Migraine and Headache Endpoint Definitions

[figure not shown]
Diagnosis	Definition/Criteria
Migraine headache	A headache, with or without aura, of ≥30 minutes duration with both of the following required features (A and B):  A. At least 2 of the following headache characteristics:
	Unilateral location
	Pulsatile quality
	Moderate or severe pain intensity
	Aggravation by or causing avoidance of routine physical activity
	AND
	B. During headache at least one of the following:
	Nausea and/or vomiting
	Photophobia and phonophobia
	(Definition adapted from the Standard International Headache Society [IHS] International Classification of Headache Disorders (ICHD)-3 beta)

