5.2. Determination of Sample Size

The study will enroll approximately 825 patients. Eligible patients will be randomized in blinded fashion in a 2:1:1 ratio to placebo (approximately 413 patients), LY2951742 120 mg/month (target of 206 patients), or 240 mg/month (target of 206 patients). With the assumption of a 26% discontinuation rate and an effect size of 0.33 in the last month of the 6-month treatment phase, it is estimated that this sample will provide approximately 95% power that at least 1 dose of LY2951742 will separate from placebo at a one-sided 0.025 significance level based on simulations using Dunnett test. Assumptions were based on data from 2 double-blind, placebo-controlled, Phase 2 studies, with adjustment to reflect the longer treatment duration and greater variability expected in a larger, multi-country, Phase 3 study.

^aPatients randomized to the 120 mg dose will receive a loading dose of 240 mg at the first injection only (Visit 3). Abbreviations: SP = study period.

Approximately 1557 patients may be screened to ensure randomization of 825 patients, with an estimated 611 patients completing the study.

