Number of moderate-severity headache days		
Number of headache hours		
Number of ICHD migraine headache days		
PGI-S		
PGI-I (adjusting for PGI-S)		
Average Pain Score for non-migraine chronic pain		
Mean severity of migraine headache		
Number of migraine headache days with nausea and/or		
vomiting		
Number of migraine headache days with photophobia and		
phonophobia		
Number of migraine headache days with aura		
Number of migraine headache days prodrome symptoms		
other than aura		
Number of non-migraine headache days with aura		
Proportion of aura among migraine attacks		
Number of days with abortive medication use		MMRM for SP
Number of classes of abortive medication use	MMRM	III/IV
Number of classes of abortive medication use on migraine		111/1 (
headache days	_	
Average number of classes of abortive medications use		
Average number of classes of abortive medications use on		
migraine headache days	_	
Number of days with triptans use	_	
Number of migraine headache days with triptan use	_	
Number of days with NSAIDs/aspirin use		
Number of migraine headache days with NSAIDs/aspirin		
use		

Secondary and Exploratory Efficacy Variables and Analysis Methods (cont)

Efficacy Variables	Analysis in SP III	Analysis in SP III/IV
Number of days with NSAIDs/aspirin use		
Number of migraine headache days with NSAIDs/aspirin		
use		
Number of days with acetaminophen/paracetamol use		
Number of migraine headache days with		
acetaminophen/paracetamol use		
Number of days with ergots use		
Number of migraine headache days with ergots use		
Number of days with anti-nausea medication use		
Number of migraine headache days with anti-nausea		
medication use		
Number of days with Multi-Class abortive medication use		
Number of migraine headache days with multi-class		
abortive medication use		
Average number of abortive medication classes		
Average number of abortive medication classes on migraine		
headache days	CI D O OV	CL D O GV
X% response rate (X=30, 50, 75, or 100) (visit wise)	GLIMMIX	GLIMMIX
50% response sustained for 3 consecutive months until	Logistic regression	NA
patient's endpoint in 6-month treatment phase		
50% response sustained from month 1 to month 6	ar n n arr	
Distribution of managements in CD III	GLIMMIX (to get	NI/A
Distribution of response rate in SP III	estimated response rates)	N/A
	Kaplan-Meier	
Time to first 50% response in SP III	curve and stratified	N/A
Time to first 3070 response in St. III	log-rank test	14/11

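### The non-migraine chronic pain score averages whichever conditions are reported, so its change from baseline mixes change in pain with change in the list of conditions

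*SAP*

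**What the plan says.** Protocol Table CGAH.1 lists as a tertiary endpoint: "Mean change from baseline in average pain severity of other chronic pain conditions". SAP Table 4.3 carries the same endpoint as exploratory. SAP 5.4.2.2 gives the form and the derivation:

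- The gate question is in the present tense: "Q1: Does the subject have any non-migraine chronic pain conditions". Only a Yes leads to the two further questions.
- The second question identifies the condition by an adverse event number or a medical history number.
- The third asks for average pain over the past week, from 0 (no pain) up to "10 Worst pain imaginable".
- The patient's score is obtained by "averaging the pain scores of all reported non-migraine chronic pain conditions".
- The quantity to be analysed follows from that score: "The mean change from baseline in the average pain score will be used as the analysis value".
- There is one supplementary analysis, for a condition "reported by more than 15% of the study population at baseline, the pain score of that specific condition will also be analyzed".

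The Schedule of Activities (Protocol Appendix 2) places the assessment at Visits 3, 7 and 12 and at early termination; a footnote says a clinician administers it. SAP Table 5.6 lists "Average Pain Score for non-migraine chronic pain" among the variables analysed by MMRM.

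Neither document limits the average to conditions present at baseline. Neither says how to score a condition that has resolved, a condition that is new, or a visit at which the gate question is answered No.

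**The concern.** A change from baseline in a mean is interpretable when the same items are averaged on both occasions. Here the items are whatever is reported. Repeating the assessment and analysing change from baseline implies that the average is taken afresh at each visit over that visit's list. The list can shrink when a condition resolves. It can grow when a new pain appears: Protocol 8.2 has new conditions recorded as adverse events, and the form accepts an adverse event number.

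At stake is the sign of an individual patient's change. A patient who acquires an additional pain can be recorded as improved, and a patient who loses one can be recorded as worse. A patient whose only pain disappears may have no value at that visit. Such a gap would depend on the unobserved outcome, whereas SAP 5.5.1.2 rests the repeated-measures estimates on data missing at random.

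The SAP handles a comparable case explicitly. For mean severity of remaining migraines, SAP 5.4.1 states that a period with no migraine headache days gives a missing value, and SAP 5.5.10.3 treats the measure as conditional. The pain score has no corresponding rule.

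**Working it through.** The documents give no figure to reproduce for this score. The check applies the written rule to assumed scores.

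**Inputs.** The rule (mean of reported scores, follow-up minus baseline) and the 0 to 10 range come from SAP 5.4.2.2. The individual scores are assumptions. Let a patient have k conditions with mean m at baseline, all other scores unchanged.

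**Formulas.**

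- New condition with score s added: change = (km + s)/(k + 1) - m = (s - m)/(k + 1). This is negative, an apparent improvement, whenever s < m.
- Condition with score s resolves and is no longer listed (k at least 2): change = (km - s)/(k - 1) - m = (m - s)/(k - 1). This is positive, an apparent worsening, whenever s < m.
- Condition with score s resolves and stays listed at 0: change = -s/k, always an improvement.

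**Numbers.** The last column uses baseline conditions only, with confirmed resolution scored 0.

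| Event | Scores | Change under the written rule | Change over baseline conditions |
|---|---|---|---|
| New milder pain | {8} to {8, 2} | 5 - 8 = -3 | 8 - 8 = 0 |
| New more severe pain | {4} to {4, 8} | 6 - 4 = +2 | 4 - 4 = 0 |
| Milder condition resolves, not listed | {8, 2} to {8} | 8 - 5 = +3 | (8 + 0)/2 - 5 = -1 |
| Milder condition resolves, listed at 0 | {8, 2} to {8, 0} | 4 - 5 = -1 | -1 |
| Only condition resolves, gate answer No | {6} to none | not defined | 0 - 6 = -6 |

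**Range.** There are 45 pairs of integer scores from 1 to 10 with one condition milder than the other (a > b). Over these pairs:

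- adding the milder condition gives (b - a)/2, from -0.5 to -4.5;
- resolution of the milder one gives (a - b)/2, from +0.5 to +4.5, if it is no longer listed;
- the same resolution gives -b/2, from -0.5 to -4.5, if it is kept at 0.

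With the set fixed at baseline and confirmed resolution scored 0, the last range applies throughout, so resolution of the milder condition never counts as worsening.

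**Does the condition-specific analysis cover this?** Only for common conditions. With the planned size ("The study will enroll approximately 825 patients"), 0.15 x 825 = 123.75, so at least 124 patients must report the same condition at baseline. That analysis does not mix conditions, but it too has no rule for resolution.

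**Gate answer No.** SAP Table 5.5 requires a baseline and at least one post-baseline observation. If No is treated as missing, a patient answering No at every follow-up leaves the analysis, while one who resolves between Visits 7 and 12 still contributes Visit 7. Where the LOCF-endpoint ANCOVA of SAP 5.5.10.3 is applied to this score, that second patient would carry the Visit 7 score forward.

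**The case against.** The strongest objection is that the SAP does not say a resolved condition leaves the average. Zero is an allowed score, each entry is tied to a record number, and a site could keep a known condition listed at 0. Resolution is then scored correctly in direction. This stands: the apparent worsening is conditional on the condition no longer being reported. That is the natural reading of a present-tense gate question, but it is not stated, and the form's completion instructions are not in these documents. It also requires that another condition remains, that the resolved one scored below the patient's mean, and that the others do not fall enough to offset it.

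The objection does not reach the new-condition case. Averaging everything reported makes a new pain below the existing mean lower the score, with no further assumption except that other scores do not rise enough to offset it.

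A reader might infer that complete responders are removed, that the objective cannot be answered, or that any real benefit is hidden. The documents do not support these readings. Patients whose list is stable are scored correctly. MMRM uses every observed post-baseline visit, so a missing visit does not by itself remove a patient. Changes in the list can occur in every arm and move the score either way, and nothing shows a difference between arms.

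A further objection is to the obvious remedy: scoring 0 whenever a condition is not mentioned would turn a clinician's omission into complete relief. This also stands, and the fix below allows for it.

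**Conclusion.** The derivation is flawed, not merely short of detail: the score averages over a set that may change between visits, so its change mixes pain with list composition. For two conditions scored 1 to 10, the artefact from adding a milder pain is -0.5 to -4.5 points. Resolution of a milder condition gives +0.5 to +4.5 or -0.5 to -4.5, depending on a listing convention that the SAP does not state. Two sites could therefore record the same outcome as +3 or -1.

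It would be too strong to say that a mild condition resolving counts as worsening without qualification, because the permitted zero can reverse the sign.

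These sizes are for single patients with assumed scores. The documents do not say how many patients have several conditions or how often lists change, so the size and direction of any between-arm bias cannot be estimated. The endpoint is exploratory, outside the multiplicity-controlled family, and does not touch the primary or key secondary conclusions. The change is desirable but not essential.

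**What to change.** Amend SAP 5.4.2.2 as follows:

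- Derive the change over the conditions present at baseline only, matched across visits by the adverse event or medical history number on the form. Protocol 8.2 has changes in pre-existing conditions recorded as adverse events, so matching must allow for a baseline condition that reappears under a new number.
- Score a baseline condition 0 at a completed assessment where the gate question is answered No, or where the condition is confirmed as no longer present.
- Treat unexplained non-reporting as missing, and score it 0 in a sensitivity analysis. A missing condition should not be dropped from the follow-up mean alone, which would bring the artefact back.
- Tabulate newly reported conditions separately by arm.

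The cost is derivation wording and some number matching, which may need review because the SAP does not say that the number is re-entered at every visit. The downside is that new conditions no longer enter the mean-change score and appear only in the table. Protocol 9.2 allows SAP changes only before unblinding, so the amendment has to precede it.
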